4.2. Subject Selection

Subjects of both genders meeting all the inclusion criteria and none of the exclusion criteria are eligible for the study.

Inclusion Criteria:

- Patient is at least 18 years of age
- Patient's heart rate meets at least **one** of the following:
 - Patient has a sinus rate ≤ 50 **OR** a junctional escape rhythm no faster than 50
 - Patient has a history of exercise intolerance
- Patient complains of general fatigue, shortness of breath, shortness of breath with exertion, syncope, light headed dizziness, palpitations, lethargy, dyspnea **OR** malaise within the last 30 days that are not related to other discovered causes (such as untreated hypothyroidism or anemia).
- Patient (or patient's legally authorized representative) is willing and able to sign and date written Patient Consent Form/Patient Data Release Consent

Exclusion Criteria:

[figure not shown]
- Patient has recent history of blood loss
- Patient has a medical history leading to suspicion of neurological disorder
- Patient has a history of Chronic Atrial Fibrillation
- Patient is enrolled or planning to participate in a concurrent drug and/or device study at any time during the course of this clinical study without documented pre-approval from the Medtronic study manager
- Patient is not expected to survive for 12 months
- Patient is anticipated to be unwilling or unable to comply with the clinical investigation plan

Subjects will be screened to ensure they meet all of the inclusion and none of the exclusion criteria. Subjects are considered enrolled upon signing the Informed Consent Form/Patient Data Release.

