5.6. Study Exit

Subjects may be exited from the study for any of the following situations, including but not limited to:

- Subject does not meet an indication for pacing therapy
- Subject meets an indication for pacing but not a SND indication for pacing therapy

- Subject has met a SND indication for pacing therapy but will not be receiving pacing therapy
- Subject diagnosis meets an SND indication for IPG Therapy and a non-Medtronic/Vitatron device was implanted.
- Completion of study follow-up with no diagnosis made
- Study Closure
- Subject lost to follow-up, patient doesn't come back after baseline for diagnosis test decision
- Subject death
- Subject did not meet inclusion/exclusion criteria
- Subject chooses to withdraw (e.g., consent withdrawal, relocation to another geographic location)
- Investigator deems withdrawal necessary (e.g., medically justified, failure of subject to maintain adequate study compliance)

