11.1. Primary Objective(s)

Primary Objective #1

Evaluate the impact of the intervention on the diagnosis of SND.

Hypothesis

The primary objective will be tested with the following hypothesis:

$$H_0: p_{1t} = p_{2t}$$

$$H_A: p_{1t} \neq p_{2t}$$

where p_{1t} is the proportion of patients with SND in Phase I and p_{2t} is the proportion of patients with SND in Phase II at time point t .

Endpoint Definition

The absolute change in the proportion of subjects diagnosed with SND at pre-specified time points ($\% = \text{number diagnosed} / \text{number enrolled} \times 100$ at time point $t = 6$, or t is a multiple of 6 representing any additional 6-month interval for which there is sufficient follow-up information) and the absolute change in the number of subjects diagnosed with SND per person-year.

Analysis Methods

A. Statistical Methodology

To compare the proportion of subjects with an SND diagnosis pre-intervention (Phase I) to the proportion post-intervention (Phase II), a binomial exact test will determine statistical significance. The proportion of subjects diagnosed will be evaluated at multiple time points because the time to diagnosis is expected to vary by hospital. Thus, times are pre-specified starting at 6 months and any additional 6-month interval thereafter for which there is sufficient follow-up data available to compare study phases. Proportions calculated at all available time points will be reported. Additionally a Poisson regression will compare the average number of subjects with an SND diagnosis in Phase I and Phase II where the subject time in study is treated as an offset in the model. The above described tests will be performed separately within site as well as overall.

B. Determination of Patients/Data for Analysis

All subjects that are enrolled in the study and that meet study inclusion/exclusion criteria will be included in the determination of the proportion estimates. The proportion estimates will be calculated based on information from fixed time points at 6 months of follow-up, and any additional 6-month interval thereafter for which there is sufficient follow-up data available to compare study phases. The number of subjects that obtain a SND diagnosis by pre-specified time point t is included in the numerator and the number of subjects enrolled is included in the denominator.

Sample Size Methods and Assumptions

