The proportion of SND diagnoses in subjects with bradycardia is currently unknown. The power calculations conservatively assume that the SND diagnosis will be 10% at six months of follow-up, or equivalently an SND incidence of 0.2 diagnoses per person-year. If 200 subjects are collected each in Phase I and in Phase II, assuming a type I error of 0.05 and power of 0.80, a binomial exact test will detect an increase in SND diagnosis of at least 10%. For example, the study will find a statistically significant difference between a Phase I SND percentage of 10% at 6 months and a Phase II SND percentage of 20% at 6 months. If the proportion of SND diagnoses is smaller than 10%, there will be more power to detect significant differences in the diagnosis proportion. It is expected that the study attrition rate may be 5% of the study population. To account for attrition, the sample size for Phase I will be a minimum of 210 subjects and for Phase II will be a minimum of 210 subjects.

Primary Objective #2

Evaluate the impact of the intervention on SND subjects receiving a referral for an indicated IPG device.

Hypothesis

The primary objective will be tested with the following hypothesis:

$$H_0: p_{1t} = p_{2t}$$

$$H_A: p_{1t} \neq p_{2t}$$

where p_{1t} is the proportion of patients referred for an IPG in Phase I and p_{2t} is the proportion of patients in Phase II at time point t .

Endpoint Definition

The absolute change in the proportion of subjects receiving therapy referral for an indicated IPG at pre-specified time points ($\% = \text{number receiving IPG}/\text{number with SND diagnosis} \times 100$ at time point t where $t = 3, 6$, and any additional 3-month interval for which there is sufficient follow-up information) and the absolute change in the number of subjects implanted per person-year.

Analysis Methods

Statistical Methodology

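### Primary Objective #1 has two denominators, all enrolled and enrolled-and-eligible, and the plan does not limit the eligibility judgement to what was known at enrollment

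*Combined protocol and SAP*

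**What the plan says.** Section 11.1, Primary Objective #1, describes the denominator three times.

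- The endpoint definition divides the number diagnosed by the number enrolled.
- Part B, first sentence: "All subjects that are enrolled in the study and that meet study inclusion/exclusion criteria will be included in the determination of the proportion estimates".
- Part B, last sentence: "the number of subjects enrolled is included in the denominator".

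Other sections bear on whether these are the same people.

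- Sections 4.2 and 5.3 make a subject enrolled when the consent or data release is signed.
- Section 5.6 lists, among reasons for exit, "Subject did not meet inclusion/exclusion criteria".
- One inclusion criterion in section 4.2 requires symptoms "that are not related to other discovered causes (such as untreated hypothyroidism or anemia".
- Section 5.3 expects enrollment before the final diagnosis is known. Table 1 and section 5.4 have diagnostic testing continue afterwards.
- Section 4.3 introduces the toolkit after Phase I and says it may contain diagnostic algorithms.
- Sections 4.2, 4.4 and 5.3 provide for screening against the criteria before enrollment, with screening logs.

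No section says at what point eligibility is fixed for the analysis, who decides it, or whether that decision is blind to phase or diagnosis.

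**The concern.** Two analysts could follow section 11.1 faithfully and report different primary percentages. That alone needs correcting for a primary endpoint.

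The narrower set also leaves an opening. A subject whose symptoms turn out after consent to have another cause could be judged not to have met the symptom criterion. Such a subject will usually not carry an SND diagnosis, so removal shrinks the denominator and leaves the numerator alone. If this happened to the same extent in both phases, both percentages would rise together. If it happened more in one phase, that phase would look better at diagnosing SND without having diagnosed anyone more. The study compares two periods without randomization and the intervention acts on the work-up itself, so the denominator should not depend on what the work-up finds.

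**Working it through.** **1. The plan's own figure.** Inputs from section 11.1: "a Phase I SND percentage of 10% at 6 months and a Phase II SND percentage of 20% at 6 months"; "assuming a type I error of 0.05 and power of 0.80"; two-sided alternative. The pooled normal approximation is

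n = [z(0.975)·√(2·p̄·(1−p̄)) + z(0.80)·√(p1(1−p1) + p2(1−p2))]² / (p2−p1)²

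With p̄ = 0.15: n = [1.960·√0.255 + 0.842·√0.25]² / 0.01 ≈ 199 per phase. Power at 200 per phase is 0.802. This reproduces the plan's 200. For attrition ("It is expected that the study attrition rate may be 5% of the study population"), 200 × 1.05 = 210 and 200/0.95 ≈ 211, so 210 is reproduced too. (The match is to the normal approximation. Two-sided Fisher, by full enumeration, gives power 0.768 at 200 and 0.792 at 210. That is a separate matter.)

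**2. Planned power hardly depends on the denominator.** For 10% versus 20%, Fisher power is 0.792 with all 210 per phase. It is 0.792, 0.798 and 0.805 when 5%, 10% or 20% of subjects, all undiagnosed, are removed from both phases.

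**3. Effect of removal on the percentage.** Let p be the true share diagnosed among all enrolled and f the share removed, all undiagnosed. The percentage among those kept is p/(1−f).

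- p = 10%: f = 10% gives 0.10/0.90 = 11.1%; f = 20% gives 0.10/0.80 = 12.5%.
- p = 20%: f = 10% gives 0.20/0.90 = 22.2%; f = 20% gives 0.20/0.80 = 25.0%.

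**4. Effect on type I error.** Assumptions: 210 enrolled per phase, the same true rate in both phases, only undiagnosed subjects removed, and the named binomial exact test taken as two-sided Fisher at 0.05. Rejection probabilities come from full enumeration. The removal shares are not in the documents, so a range is shown. In this table the number removed is fixed and the number diagnosed is binomial out of 210.

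| Removed, Phase I vs Phase II | True 10% | True 20% |
|---|---|---|
| 0% vs 0% | 3.5% | 3.8% |
| 5% vs 5% | 3.5% | 3.8% |
| 10% vs 10% | 3.5% | 4.0% |
| 0% vs 5% | 4.4% | 5.0% |
| 5% vs 10% | 4.8% | 5.5% |
| 10% vs 15% | 4.9% | 5.7% |
| 0% vs 10% | 5.4% | 7.7% |
| 0% vs 20% | 10.6% | 19.9% |

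A slightly different model treats the diagnosed count as binomial with n = 210(1−f) and rate p/(1−f). With nobody removed in Phase I and 10%, 15% and 20% removed in Phase II, it gives 5.4%, 7.6% and 10.4% at a true 10%, and 7.5%, 12.0% and 19.5% at a true 20%. The two models agree closely.

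**5. Direction.** In the 0% vs 20% row nearly all rejections favour Phase II: 10.36 of 10.62 points at a true 10%, and 19.84 of 19.93 at a true 20%. By symmetry, 20% vs 0% gives the same error in favour of Phase I.

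**The case against.** The two sentences have an ordinary reading that reconciles them. The first sets the population, and the last says that within it the diagnosed are divided by the enrolled rather than by, say, those who completed follow-up. On this view eligibility means status as screened, and screening comes before consent. The exit reason in section 5.6 is in the past tense, which fits a subject enrolled in error. The same list has other exits for a subject whose work-up points away from SND, such as having no pacing indication or finishing follow-up undiagnosed, and those exits leave the subject in the denominator under either sentence. The discovered causes in section 4.2 can be read as causes already known at screening.

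A reader might infer that the primary comparison is biased toward the intervention, through exclusions made by unblinded investigators. The documents do not support that. They never say that work-up findings will remove subjects, never say who decides membership of the analysis set, and give no removal rates. That inference needs more removals in Phase II. Ancillary Objective #4 anticipates that the intervention may change screening, and better screening could mean fewer ineligible enrollees in Phase II, which would push the other way. The only loss figure in the plan is 5% attrition, which is not an ineligibility rate.

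Much of this stands, and the bias must be stated conditionally. What remains is that the plan does not state the reconciling reading, section 5.6 itself foresees enrolled subjects who fail the criteria, and nothing fixes the eligibility judgement at enrollment.

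**Conclusion.** The inconsistency is literal and concerns the primary endpoint, so it should be corrected before analysis. Distortion of the phase comparison is possible, not planned or shown. Its size depends on how far removal differs between phases: essentially none if removal is equal, small at 5 points, and material at about 15 points or more (from about 10 points if the true rate is 20%). The large figures all rest on removing nobody in Phase I and only undiagnosed subjects in Phase II, which is the unfavourable corner of the range. The case for acting does not depend on that corner. The rule contradicts itself, the plan's own endpoint definition already supplies the answer, and adopting it closes the route whatever the removal rates turn out to be.

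**What to change.** - Make all enrolled (consented) subjects the primary denominator for Objective #1, including those later exited for not meeting the criteria. Amend the first sentence of part B to agree with the endpoint definition and the last sentence.
- Give the criteria-based set as a sensitivity analysis, limited to violations evident from data recorded before enrollment.
- Report eligibility exits by phase and by reason, so that a reader can see whether removal differed.
- While editing, check the analysis sets for Primary Objective #2 and the secondary objective, which mention only the inclusion criteria.

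Cost: a few sentences, with no new data, visits or subjects. The downside is slightly lower percentages, because a few subjects enrolled in error stay in the denominator. Excluding them from the primary set on pre-enrollment data alone would also close the route, but it would mean changing the endpoint definition instead of following it.

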4. METHODOLOGY

The Brady MX study is a prospective, sequential, post market study with an educational phase and any market released pacemaker from the Medtronic family of devices may be used in this study. It is hypothesized that the use of a practice-specific process improvement intervention consisting of education, diagnostic algorithm(s) and

documentation tools that advocate and reinforce adherence to consensus treatment guidelines will improve the quality of care for patients with sinus node dysfunction (SND). The study will be conducted in two phases, with Phase I serving as control subjects and Phase II measuring the impact of the intervention.

The study will be conducted in compliance with the Clinical Investigation Plan, Clinical Trial Agreement, approved labeling, latest version of the Declaration of Helsinki, and laws and regulations of the country in which the study is conducted, including data protection laws.

Principles of the Declaration of Helsinki have been incorporated into this study by means of the patient informed consent/Patient Data Release process, IRB/MEC approval (if required); study training, clinical trial registration, risk benefit assessment, and publication policy, etc.

The study may enroll up to 500 Mexican subjects. with at least 210 subjects enrolled per study phase. Once enrolled, Phase I subjects should be followed for approximately 6 months and Phase II subjects should be followed for approximately 6 months. Brady MX is anticipated to be completed in mid-2018.

Subject data will be collected at enrollment/baseline, diagnostic assessment visits and implant visit. Data will continue to be collected until one of the exit criteria has been met. Brady MX does not mandate specific requirements regarding any other procedures, subject visits to the clinic, clinical treatment of subjects or device programming. Clinical data will be collected using electronic case report forms.

Centers will be eligible to enroll subjects in Brady MX upon Medtronic's receipt of required center activation materials and written approval.

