4.3. Study Design

There are two phases for Brady MX

Figure 1: IMPROVE Brady Study Design

Phase I: This phase of the study serves as a control period. During Phase I physicians will assess and treat subjects per their site’s standard care practice.

Enrollment for Phase I is anticipated to occur for approximately 6 months but will continue until a minimum of 210 subjects have been enrolled. For subjects enrolled during Phase I, collection of diagnostic assessment and implant data will be complete 6 months after the last enrollment. At that time, all Phase I subjects will be exited

Phase II:
The objective of the Brady MX study is to provide investigators with comprehensive resources that may be adapted by the Principal Investigator and his/her colleagues to create a practice specific process improvement intervention to improve the quality of care for patients.

At the completion of Phase I, the Principal Investigator and co-investigators will complete an educational workshop and be given access to the Brady MX toolkit. In addition, the Principal Investigator and his/her colleagues are encouraged to adapt tools from the Brady MX toolkit to create a practice specific process improvement intervention.

Immediately following completion of the educational workshop, study investigators will receive written authorization from Medtronic that they are authorized to enroll subjects in Phase II. Enrollment during this phase is anticipated to occur for approximately 6 months but will continue until a minimum of 210 subjects have been enrolled.

The Brady MX process improvement intervention toolkit may include an education workshop, diagnostic algorithm(s), patient video and tools for investigators to educate their patients on their disease state, available therapy options, and benefits and risks associated with the therapy options.

For subjects enrolled during Phase II collection of diagnostic assessment data will be complete 6 months after last enrollment. At that time, any subjects without a diagnosis will be exited from the study.

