To compare the proportion of SND subjects that receive a referral for indicated therapy pre-intervention (Phase I) to the proportion post-intervention (Phase II), a binomial exact test will determine statistical significance. The proportion of subjects diagnosed will be evaluated at multiple time points because the time from diagnosis to implant is expected to vary by hospital. Shorter time intervals will be used to evaluate the proportion of referrals than for the proportion of diagnosis because implants typically occur more quickly than the SND diagnosis. Thus, times are pre specified starting at 3 months and any additional 3-month interval thereafter for which there is sufficient follow-up data available to compare study phases. Proportions calculated at all available time points will be reported. Additionally, a Poisson regression will compare the average number of subjects with an implant where the subject time in study beginning at the time of SND diagnosis is treated as an offset in the model.

Determination of Patients/Data for Analysis

The number of subjects that meet inclusion criteria and obtain an SND diagnosis shall be included in this analysis. The proportion estimates will be calculated based on information from fixed time points at 3 months of follow-up, 6 months of follow-up, and any additional 3-month interval thereafter for which there is sufficient follow-up data available to compare study phases. The number of subjects that obtain an IPG referral by pre-specified time point $t = 3, 6, \text{ etc.}$, will be included in the numerator and the number of subjects with an SND diagnosis will be included in the denominator.

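### Referral and implant proportions divide by all SND-diagnosed subjects, so subjects diagnosed late count as not referred or not implanted; for diagnosis itself, only time points of 12 months or later are affected

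*Combined protocol and SAP*

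**What the plan says.** For Primary Objective #1, Section 11.1 defines the proportion at 6 months and at "any additional 6-month interval thereafter for which there is sufficient follow-up data available to compare study phases". Diagnoses are counted cumulatively up to t, but the divisor stays the same whatever the time point: "the number of subjects enrolled is included in the denominator".

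For Primary Objective #2 the times are 3 months, 6 months and further 3-month steps, and "the number of subjects with an SND diagnosis will be included in the denominator". Section 11.2 uses the same denominator for implant. Neither section says whether t for these proportions runs from enrollment or from diagnosis. The accompanying Poisson model starts its time offset at SND diagnosis. For each objective an exact binomial test on the proportions decides significance, and the Poisson model is additional.

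Section 4.3 fixes the end of observation. In Phase I, "collection of diagnostic assessment and implant data will be complete 6 months after the last enrollment". For the second phase, "For subjects enrolled during Phase II collection of diagnostic assessment data will be complete 6 months after last enrollment"; that sentence does not mention implant data. Accrual length is open: "Enrollment for Phase I is anticipated to occur for approximately 6 months but will continue until a minimum of 210 subjects have been enrolled", with the same rule in Phase II. Section 4 describes follow-up more briefly: "Phase I subjects should be followed for approximately 6 months", and likewise for Phase II.

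No censoring method or at-risk restriction is given for any of the proportions.

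**The concern.** A crude proportion at time t is a fair estimate only if everyone in the denominator could be observed to t. Under Section 4.3 a subject's potential follow-up is 6 months plus however early he or she enrolled. That covers 6-month diagnosis. It does not cover referral or implant 3 or 6 months after a diagnosis that may itself come late.

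Subjects whose observation stops before t stay in the denominator as failures. The proportion is then too low, by an amount set by accrual length and by when diagnoses occur. The intervention is meant to change diagnosis. If Phase II subjects are diagnosed sooner, they have longer post-diagnosis observation, and crude referral can rise without any change in referral practice. Part of an effect on Objective #1 could then reappear as an effect on Objective #2.

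**Working it through.** **Plan's own figures.** 10% at 6 months at a constant rate gives −ln(0.90)/0.5 = 0.211 diagnoses per person-year. The plan states 0.2, which returns 1 − exp(−0.1) = 9.5%. The normal-approximation sample size for 10% against 20% (two-sided 0.05, power 0.80) is 199 per phase; the plan states 200. Both rest on 6-month diagnosis.

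**Assumptions added here.** Uniform accrual over 6 months, closure 6 months after the last enrollment for all data in both phases, constant rates, and no early exit. Potential follow-up F is then uniform on 6 to 12 months. The monthly rate is 0.211/12 = 0.01756, so over 6 months the cumulative rate is 0.10536.

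**Time left after diagnosis (t from diagnosis).**
- Diagnosed before closure: 1 − (0.90 − 0.81)/0.10536 = 14.58% of enrolled.
- Diagnosed with at least 3 months left: 1 − (0.94868 − 0.85381)/0.10536 = 9.96%. Share: 9.96/14.58 = 68%, so about 32% have less.
- Diagnosed with at least 6 months left: 1 − (1 − 0.90)/0.10536 = 5.09%. Share: 5.09/14.58 = 35%, so about 65% have less.

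If Section 4's figure of about 6 months per subject were applied literally, practically nobody diagnosed after enrollment would have 6 months left.

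**Effect on referral.** With G the time left after diagnosis and ρ = ln 2 / median time to referral, the crude proportion averages 1 − exp(−ρ·min(G, t)) over diagnosed subjects. The true value is 1 − exp(−ρt). The documents give no referral times, so the medians are assumptions. Results are by simulation.

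| Median to referral | t | Crude | True |
|---|---|---|---|
| 2 months | 3 months | 56% | 65% |
| 2 months | 6 months | 69% | 87.5% |
| 3 months | 3 months | 43% | 50% |
| 3 months | 6 months | 57% | 75% |
| 1 week | 6 months | 96 to 97% | about 100% |

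**Dependence on when diagnosis occurs.** Keep the 3-month median and t = 6, so true referral is 75% throughout. At 0.211 diagnoses per year the crude figure is 56.5%. At −ln(0.80)/0.5 = 0.446 per year, which is the plan's 20% at 6 months, it is 57.4%. At 2 per year it is 63%, and at 6 per year 71%. The direction is systematic, but the plan's own effect, read as a higher constant rate, moves it by only 0.9 points. A large movement needs a large shift towards early diagnosis. Lengthening accrual from 6 to 12 months at 0.211 per year moves it from 56.5% to 61.4%.

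**If t runs from enrollment instead.** Subjects diagnosed after t still sit in the denominator. At t = 6 they are 1 − 10/14.58 = 31% of those diagnosed. At t = 3, where 5.13% of enrolled are diagnosed (1 − 0.94868), they are 1 − 5.13/14.58 = 65%. All count as failures unless referral preceded diagnosis.

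**Objective #1.** At 6 months everyone has the required potential follow-up, so crude and true agree at 10.0%. At 12 months the true value is 1 − 0.81 = 19.0%. The crude value is 14.6% with 6 months of accrual, 15.7% with 8, 16.1% with 9 and 16.8% with 12. With no true effect and 210 per phase, Fisher's exact test rejects 3.7% of the time with equal 6-month accrual, 4.6% with 8 against 6 months, and 7.5% with 12 against 6.

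**The case against.** The strongest reply has four parts.

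- **The sufficiency condition.** Later time points are used only where follow-up supports a comparison. With 6-month accrual essentially nobody reaches 12 months, so a reasonable reading drops that time point for diagnosis. This stands for Objective #1. It does not help Objective #2 or implant, where 3 and 6 months are named outright. The condition is also undefined, and it leaves unchanged the denominator of any time point that is used.
- **Poisson regression accounts for exposure.** It does, but it is supplementary to the exact test. Under Objective #2 it counts implants, so referral has no exposure-adjusted analysis.
- **The time origin is unstated, so the bias is not established.** The size does depend on the origin. Starting at enrollment does not remove the problem while all diagnosed subjects remain in the denominator. It would largely do so at 3 and 6 months only if the denominator were cut to subjects diagnosed by t, which the text does not say.
- **Referral may follow diagnosis at once.** Table 1 records final diagnosis and treatment decision at the same type of visit. If the typical gap is a week, the shortfall is only 3 to 4 points. This stands as a limit on size for referral. Implant can follow later.

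A reader might also infer that unequal accrual could by itself produce a significant result on Objective #1. The documents do not support that for the planned conduct. The powered 6-month comparison is untouched. About 6 months of accrual is anticipated in each phase, and Section 1.2 expects about 26 months in total. If the phases run one after the other, 12 plus 6 months of accrual plus two 6-month follow-ups is already 30 months. At 8 against 6 months the rejection rate barely moves.

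**Conclusion.** The point holds for Primary Objective #2 and the secondary objective. Their proportions count unobserved time after diagnosis as failure, at the first time points the plan names. On the stated assumptions about a third of diagnosed subjects lack 3 months of post-diagnosis observation and about two thirds lack 6. The resulting shortfall in 6-month referral ranges from 3 to 4 points (1-week median) to 18.5 points (87.5 − 69, 2-month median). A false phase difference is possible if diagnosis becomes earlier or accrual differs, but it is small under the plan's own 10% to 20% effect at constant rates.

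For Objective #1 the point is limited to 12 months and later, if those times are used at all. There both phases are biased downward, and the difference is distorted materially only if accrual times differ a lot. Subjects exited early because they have no pacing indication would make the true 12-month shortfall smaller than the constant-rate model shows.

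The plan should be changed, but its powered comparison is not in question on this ground.

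**What to change.** - State that t for referral and implant runs from SND diagnosis.
- Estimate and compare both at each t by Kaplan-Meier or cumulative incidence from diagnosis, censoring at administrative closure. Keep subjects exited after a decision not to receive pacing as known non-events.
- State one closure rule for both phases, including implant data in Phase II, which Section 4.3 leaves open.
- For Objective #1 keep the crude proportion and exact test at 6 months. At a later t use cumulative incidence from enrollment, only if both phases still have subjects under observation at t; otherwise do not report that t. Subjects exited as having no pacing indication remain known non-events. This replaces the undefined sufficiency condition.

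The sample size does not change. The dates of diagnosis, implant and exit are already needed for the planned analyses; a referral date is needed for any by-t count. The cost is plan wording, standard time-to-event programming and slightly wider intervals at later times. Numbers will be small: at the plan's Phase I rate about 31 subjects are diagnosed (210 × 14.58%), of whom about 11 (35%) could be followed for a full 6 months. The crude proportion hides that limit but does not remove it.
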